## 1.0 TRIAL SUMMARY

[figure not shown]
Abbreviated Title	Radioimmunotherapy for LA-NSCLC
Trial Phase	II
Clinical Indication	Locally advanced non-small cell lung cancer
Trial Type	Single Arm, Open Label, with 2 cohorts
Type of control	None
Route of administration	Intravenous
Trial Blinding	None
Treatment Groups	PembroRT Cohort – Subjects with PD-L1 expression $\geq 50\%$ ChemoRT Cohort - Subjects with PD-L1 expression $< 50\%$
Number of trial participants	PembroRT Cohort – 25 ChemoRT Cohort – Approximately 38
Estimated enrollment period	3/1/2018 to 9/1/2019
Estimated duration of trial	18 months
Duration of Participation	28 months
Estimated average length of treatment per patient	PembroRT Cohort - One year

## 2.0 TRIAL DESIGN

### 2.1 Trial Design

This is a Phase II trial evaluating the efficacy and safety of sequential pembrolizumab (200 mg every three weeks) and accelerated, dose-painted radiotherapy for patients with locally advanced NSCLC with PD-L1 expression  $\geq 50\%$ . Patients with PD-L1 expression  $< 50\%$  will also be enrolled and treated with standard concurrent chemoradiotherapy to serve as a non-randomized comparison group.

### 2.2 Trial Diagram

### 3.0 OBJECTIVE(S) & HYPOTHESIS(ES)

#### 3.1 Primary Objective(s) & Hypothesis

(1) **Objective:** To characterize progression-free survival rates following treatment with sequential pembrolizumab and radiotherapy for locally advanced NSCLC with PD-L1 expression  $\geq 50\%$ .

**Hypothesis:** We hypothesize that sequential pembrolizumab and radiotherapy for locally advanced NSCLC with PD-L1 expression  $\geq 50\%$  prolongs progression-free survival compared to historical outcomes.

#### 3.2 Secondary Objective(s) & Hypotheses

(1) **Objective:** To characterize freedom from distant metastasis rates following treatment with sequential pembrolizumab and radiotherapy for locally advanced NSCLC with PD-L1 expression  $\geq 50\%$ .

**Hypothesis:** We hypothesize that sequential pembrolizumab and radiotherapy for locally advanced NSCLC with PD-L1 expression  $\geq 50\%$  prolongs freedom from distant metastasis compared to historical outcomes.

(2) **Objective:** To characterize freedom from intrathoracic disease progression rates following treatment with sequential pembrolizumab and radiotherapy for locally advanced NSCLC with PD-L1 expression  $\geq 50\%$ .

**Hypothesis:** We hypothesize that sequential pembrolizumab and radiotherapy for locally advanced NSCLC with PD-L1 expression  $\geq 50\%$  prolongs freedom from intrathoracic disease progression compared to historical outcomes.

(3) **Objective:** To characterize overall survival rates following treatment with sequential pembrolizumab and radiotherapy for locally advanced NSCLC with PD-L1 expression  $\geq 50\%$ .

**Hypothesis:** We hypothesize that sequential pembrolizumab and radiotherapy for locally advanced NSCLC with PD-L1 expression  $\geq 50\%$  prolongs overall survival compared to historical outcomes.

(4) **Objective:** To estimate the rate of disease progression during 3 cycles of induction pembrolizumab prior to radiotherapy for locally advanced NSCLC with PD-L1 expression  $\geq 50\%$ .

**Hypothesis:** We hypothesize that the rate of disease progression during 3 cycles of induction pembrolizumab prior to radiotherapy for locally advanced NSCLC with PD-L1 expression  $\geq 50\%$  is less than 10%.

(5) **Objective:** To demonstrate, within the limitations of a nonrandomized study, that sequential pembrolizumab and radiotherapy for locally advanced NSCLC reduces severe adverse event rates compared to standard concurrent chemoradiotherapy.

**Hypothesis:** We hypothesize that sequential pembrolizumab and radiotherapy for locally advanced NSCLC reduces severe adverse event rates compared to standard concurrent chemoradiotherapy.

(6) **Objective:** To demonstrate, within the limitations of a nonrandomized study, that sequential pembrolizumab and radiotherapy for locally advanced NSCLC does not significantly increase rates of pneumonitis compared to standard concurrent chemoradiotherapy.

**Hypothesis:** We hypothesize that sequential pembrolizumab and radiotherapy for locally advanced NSCLC not significantly increase rates of pneumonitis compared to standard concurrent chemoradiotherapy.

(7) **Objective:** To demonstrate, within the limitations of a nonrandomized study, that sequential pembrolizumab and radiotherapy for locally advanced NSCLC reduces patient-reported treatment-related toxicities compared to standard concurrent chemoradiotherapy.

**Hypothesis:** We hypothesize that sequential pembrolizumab and radiotherapy for locally advanced NSCLC reduces patient-reported treatment-related toxicities compared to standard concurrent chemoradiotherapy.

(8) **Objective:** To demonstrate, within the limitations of a nonrandomized study, that sequential pembrolizumab and radiotherapy for locally advanced NSCLC preserves physical function compared to standard concurrent chemoradiotherapy.

**Hypothesis:** We hypothesize that sequential pembrolizumab and radiotherapy for locally advanced NSCLC preserves physical function, as measured by daily step counts, compared to standard concurrent chemoradiotherapy.

(9) **Objective:** To demonstrate, within the limitations of a nonrandomized study, that sequential pembrolizumab and radiotherapy for locally advanced NSCLC reduces hospitalization rates compared to standard concurrent chemoradiotherapy.

**Hypothesis:** We hypothesize that sequential pembrolizumab and radiotherapy for locally advanced NSCLC reduces hospitalization rates compared to standard concurrent chemoradiotherapy.

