#### 4.6 Study Rationale

We hypothesize that a combination of pembrolizumab and dose-painted radiotherapy will yield improved efficacy and tolerability compared to standard chemoradiotherapy for locally advanced NSCLC patients with high ( $\geq 50\%$ ) PD-L1 expression. We will explore this hypothesis in the “pembroRT” arm of this prospective non-randomized trial. Subjects with PD-L1 expression below 50% will also be enrolled to a “chemoRT arm” and treated with standard concurrent chemoradiotherapy, to allow exploratory comparisons of toxicities and clinical outcomes following pembrolizumab and radiotherapy versus chemotherapy and radiotherapy. Subjects on both arms will use wearable fitness trackers, which will allow us to monitor closely for adverse events and demonstrate that our novel treatment approach preserves functional status compared to standard chemoradiotherapy. We will also follow patient-reported outcomes for subjects in both cohorts.

While study subjects allocated to the “chemoRT” arm of this trial based on low PD-L1 expression, will not be receiving novel therapy, we believe that the inclusion of the “chemoRT” arm in this trial is critical for several reasons:

- *To characterize outcomes following chemoradiotherapy and modern adjuvant therapy.* Since RTOG 0617 was conducted (2007-2011)[17], and even after our in-house PAINT trial (2013-2016)[33], early results from the PACIFIC trial have changed the standard of care for many patients with locally advanced NSCLC[10]. Clinicians caring for this patient population are currently in an unusual situation, where we consider treatment with one year of adjuvant durvalumab following chemoradiotherapy without published data demonstrating how this treatment affects overall survival. It is therefore important that we characterize survival rates in a contemporary patient cohort receiving chemoradiotherapy for locally advanced NSCLC. Of note, the PACIFIC trial demonstrated that the prolongation of PFS and distant metastasis-free survival with durvalumab was not influenced by PD-L1 expression. Additionally, we have not found that PD-L1 expression is a prognostic factor for patients treated with chemoradiotherapy at our institution (see figures below). While comparisons of outcomes in our two study cohorts will be limited by the non-randomized treatment allocation, outcomes in the “chemoRT” cohort will provide some frame of reference for outcomes seen in the “pembroRT” group.

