#### **4.6.2.2 Safety Endpoints**

- Severe (grade  $\geq 3$ ) adverse events, scored using CTCAE v 4.03.
  - It will be important to characterize the toxicity profile of sequential pembrolizumab and radiotherapy for locally advanced NSCLC, as this is a novel treatment approach.
- Pneumonitis (grade  $\geq 2$ ).
  - It will be important to characterize the rate of pneumonitis, which may occur because of radiotherapy or immunotherapy, for study subjects.
- Patient-reported treatment-related toxicity, scored using PRO-CTCAE.
  - See Section 4.5
- Unplanned hospitalization.
  - Many patients treated with radiotherapy or chemoradiotherapy for locally advanced NSCLC are hospitalized due to treatment toxicity. It will be important to characterize the hospitalization rate for patients treated with pembrolizumab and radiotherapy for locally advanced NSCLC.
- Daily step counts, measured using wearable fitness trackers.
  - See Section 4.4

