### 8.2 Statistical Analysis Plan – Secondary Endpoints

Time-to-event outcomes (overall survival, freedom from distant metastasis, freedom from intrathoracic progression, freedom from hospitalization) will be analyzed using the Kaplan-Meier method, from which rates at various time points and corresponding 95% confidence intervals will be estimated. Exploratory comparisons for time-to-event outcomes between the PembroRT and ChemoRT cohorts will be performed using log-rank tests. Univariate and

multivariable Cox regression models will be used to evaluate associations between time-to-event outcomes and clinical covariates, including study cohort.

Rates of radiographic responses and disease progression during induction pembrolizumab for subjects in the PembroRT cohort will be described using counts and percentages. Logistic regression models will be used to evaluate potential predictors of response or progression (e.g.: PD-L1 TPS).

Hospitalization rates and adverse event rates, scored using CTCAE as well as PRO-CTCAE, will be presented as counts and percentages. Exploratory comparisons between the PembroRT cohort and the ChemoRT cohort will be performed using chi-square or Fisher Exact testing, as appropriate.

Daily step counts throughout the study period will be presented using descriptive statistics and will be analyzed using a generalized linear mixed-model for repeated measures.

Rates of circulating tumor DNA clearance will be presented as counts and percentages, and predictors of circulating tumor DNA clearance will be explored using chi-square or Fisher exact testing, as appropriate. Exploratory analyses will be performed to evaluate PD-L1 expression, expression of alternative immune checkpoint molecules (e.g., HHLA2, B7x, and B7-H3), baseline tumor mutational burden, and markers of immune activation (e.g., expansion of T4/T8 subsets, myeloid derived suppressor cell levels, expansion of T-cell repertoire) as predictors of PFS and overall survival.

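### Objective 6 would take a non-significant test in 25 versus about 38 patients as showing no increase in pneumonitis; the difference should be estimated with a confidence interval

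*Combined protocol and SAP*

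**What the plan says.** Objective 6 in Section 3.2 is framed with the verb *demonstrate*, qualified by a reference to the nonrandomized design. What is to be demonstrated is that the regimen "does not significantly increase rates of pneumonitis compared to standard concurrent chemoradiotherapy". The paired hypothesis repeats the same absence of significance: "locally advanced NSCLC not significantly increase rates of pneumonitis compared to standard concurrent chemoradiotherapy".

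Section 4.6.2.2 makes pneumonitis of grade 2 or higher a named safety endpoint and states the aim differently: "It will be important to characterize the rate of pneumonitis, which may occur because of radiotherapy or immunotherapy, for study subjects".

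Section 8.2 does not name pneumonitis. It is covered only as one of the adverse events: "Hospitalization rates and adverse event rates, scored using CTCAE as well as PRO-CTCAE, will be presented as counts and percentages". The comparison follows: "Exploratory comparisons between the PembroRT cohort and the ChemoRT cohort will be performed using chi-square or Fisher Exact testing, as appropriate". Section 8.2 does plan intervals for time-to-event outcomes, "from which rates at various time points and corresponding 95% confidence intervals will be estimated", but pneumonitis is not among the outcomes listed there. Section 4.6 describes the purpose of the ChemoRT cohort as "exploratory comparisons of toxicities and clinical outcomes following pembrolizumab and radiotherapy versus chemotherapy and radiotherapy".

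No pneumonitis margin, expected rate, non-inferiority test, power figure or interval appears anywhere in the document.

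**The concern.** A difference test can support a claim that rates differ. It cannot support a claim that they do not, unless the result also excludes an increase large enough to matter. Objective 6 makes the non-significant result itself the finding.

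The direction of the incentive is also wrong. Objectives 5, 7 and 9 claim reductions, so low power works against them. Objective 6 claims no significant increase, so low power works for it: the smaller the cohorts, the more easily it is met.

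Pneumonitis is singled out because both radiotherapy and immunotherapy can cause it. If the plan is followed as worded, the report could state that no increase was demonstrated while the data remain compatible with a large excess. The damage would be confined to the safety conclusion; neither the primary endpoint nor patient management depends on this test.

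**Working it through.** **Inputs from the documents.** PembroRT n = 25 and ChemoRT n of about 38 (Section 8.1); binary endpoint, grade 2 or higher (Section 4.6.2.2); chi-square or Fisher test (Section 8.2).

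**Assumptions, because the documents give no values.** ChemoRT pneumonitis rates of 10% to 20%, extended to 30% as a sensitivity check; two-sided 5%, since Section 8.2 sets no level for secondary tests.

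**The plan's own figures.** There is none for pneumonitis. The cohort sizes come from elsewhere. With 40% of patients at PD-L1 of 50% or more, ChemoRT = 25 × 0.6/0.4 = 37.5, so about 38, and the total is 25/0.4 = 62.5, so about 63. The stated 81% power is for one-year PFS only. With hazards -ln(0.40) = 0.916 and -ln(0.65) = 0.431 per year, 18 months of accrual and an assumed 12 months of further follow-up, the one-sample log-rank test gives 80.6%. Neither figure bears on pneumonitis.

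**Step 1: how often a real increase goes undetected.** For each of the 26 × 39 possible outcomes (x of 25, y of 38), compute the two-sided p-value. Then sum Bin(x; 25, p1) × Bin(y; 38, p0) over the outcomes with PembroRT higher and p < 0.05. One minus that sum is the chance that no significant increase is found.

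| True rates, ChemoRT to PembroRT | Fisher | Uncorrected chi-square |
|---|---|---|
| 10% to 20% | 81% | 80% |
| 15% to 30% | 73% | 70% |
| 20% to 40% | 63% | 60% |
| 25% to 50% | 52% | 46% |
| 30% to 60% | 38% | 33% |
| 10% to 30% | 49% | 47% |
| 15% to 45% | 28% | 25% |
| 20% to 60% | 11% | 9% |

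**Step 2: what a non-significant result leaves open.** With 6/38 (16%) in ChemoRT, Fisher's test first reaches p < 0.05 at 10/25 (40%, p = 0.041). At 9/25 (36%) p = 0.078.

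The Newcombe interval for 9/25 against 6/38 combines the Wilson limits of each rate, 0.202 to 0.555 and 0.074 to 0.304, around the difference 0.360 - 0.158 = 0.202:

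- lower = 0.202 - √[(0.360 - 0.202)² + (0.304 - 0.158)²] = -0.013
- upper = 0.202 + √[(0.555 - 0.360)² + (0.158 - 0.074)²] = 0.414

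So an excess of up to 41 points is not excluded. Even near-equal observed rates, 4/25 against 6/38, give -17 to +21 points.

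**Step 3: what a margin would require.** The same enumeration gives the chance that the upper Newcombe 95% limit falls below a margin when the true rates are equal:

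| Margin | Both 10% | Both 20% | Both 30% |
|---|---|---|---|
| 15 points | 36% | 28% | 25% |
| 20 points | 56% | 44% | 40% |
| 25 points | 76% | 64% | 58% |

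For 80% power at a 15% rate (one-sided 2.5%, same cohort ratio), ChemoRT n = (1.96 + 0.84)² × 0.15 × 0.85 × (1 + 38/25)/margin². A 15-point margin needs about 75 against 113 patients, and a 10-point margin about 167 against 253.

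**The case against.** The strongest reply is that the plan never states that a non-significant test means success. Sections 4.6 and 8.2 call the comparison exploratory, Section 4.6 presents the ChemoRT adverse event rates as context for the PembroRT rates, and Section 4.6.2.2 speaks only of characterizing the rate. On that reading the trouble is one verb in Section 3.2. Counts in both cohorts will be published, so any reader can compute an interval. Low power for toxicity is also expected, because the cohort sizes come from PFS and PD-L1 prevalence.

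Much of this stands as a limit on severity. It does not remove the problem. The exploratory label and the nonrandomized qualifier deal with confounding, multiplicity and strength of claim; they do not make a non-significant test evidence of no increase. They also contradict *demonstrate*, which is a reason to reconcile the sections. That an interval could be computed later is no reason to leave it out of the plan.

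A second reply concerns the assumed rates. The statement that a doubling would more likely than not be missed holds for ChemoRT rates of 10% to 20%. It is about even at 25% (52% Fisher, 46% chi-square) and reverses at 30% (38% and 33%). That is correct and bounds the claim. The flaw in the inference does not depend on the rate.

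**Conclusion.** The concern holds. Objective 6 rests on a faulty inference rule, and at 25 against about 38 patients the rule is lenient: a true doubling from an assumed 10% to 20% would pass as no significant increase in 63% to 81% of trials by Fisher's test and 60% to 80% by chi-square. Larger excesses are caught more often; a tripling is missed in 49%, 28% and 11% of trials by Fisher's test from 10%, 15% and 20%. The percentages rest on assumed pneumonitis rates and an assumed two-sided 5% level. The absence of a margin and an interval is a matter of record. The text should be changed, but the effect is limited to one secondary safety conclusion.

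**What to change.** **Section 3.2, objective 6.** Replace with wording such as: *To estimate the difference in rates of grade 2 or higher pneumonitis between cohorts (PembroRT minus ChemoRT), recognizing that allocation was not randomized.* Reword the hypothesis as an expectation that will not be formally tested.

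**Section 8.2.** Add: *The pneumonitis risk difference will be reported with a 95% confidence interval (Newcombe). A non-significant chi-square or Fisher test will not be interpreted as showing no increase.*

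If a claim of no excess is to be kept, a justified margin must be fixed before the cohorts are compared, and the low chance of meeting it (Step 3 above) stated alongside.

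A minor addition in the same edit: objective 4 hypothesizes that the induction progression rate "is less than 10"%. Report that rate with an exact 95% interval and treat the threshold as an expectation, because even 0/25 has a two-sided upper limit of 1 - 0.025^(1/25) = 13.7%.

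**Cost.** Wording in two sections only. No additional patients, visits or data, and no change to the primary endpoint or sample size. The price is a weaker claim and a visibly wide interval in the report.

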### 3.3 Translational Objectives

(1) **Objective:** To demonstrate, within the limitations of a nonrandomized study, that sequential pembrolizumab and radiotherapy for locally advanced NSCLC with PD-L1

expression  $\geq 50\%$  increases the rate of circulating tumor DNA clearance compared to standard concurrent chemoradiotherapy.

- (2) **Objective:** To correlate PD-L1 TPS score and expression of alternative immune checkpoint molecules (e.g.: HHLA2, B7x, and B7-H3) with clinical outcomes.
- (3) **Objective:** To correlate baseline tumor mutational burden with clinical outcomes.
- (4) **Objective:** To correlate markers of immune activation and expansion of immune cell subsets with clinical outcomes.

## 4.0 BACKGROUND & RATIONALE

### 4.1 Locally Advanced Non-small Cell Lung Cancer

Lung cancer is the leading cause of cancer-related death worldwide, with more than 1.5 million deaths per year [1, 2]. More than 220,000 new cases of lung cancer are diagnosed each year in the United States. Non-small-cell lung cancer represents more than 80% of lung cancers, and about 35% of NSCLC patients present with stage III disease [3]. Standard treatment for patients with locally advanced NSCLC, which may be defined as stage III disease or unresectable stage II disease, typically consists of conventionally-fractionated (1.8-2.0 Gy/day) radiotherapy to a total dose of approximately 60 Gy with concurrent chemotherapy. This treatment approach yields median survival times of only 16-30 months and can cause significant acute and late toxicities [4-9]. The five-year survival rate following concurrent chemoradiotherapy for stage III NSCLC is approximately 20%. Outcomes for patients who are deemed unfit for concurrent chemoradiotherapy are even poorer.

In the recently published PACIFIC study [10], the anti-programmed death ligand 1 (PD-L1) antibody durvalumab was compared to placebo as consolidation therapy lasting up to 12 months in patients with stage III NSCLC without disease progression after concurrent chemoradiotherapy. Adjuvant durvalumab significantly prolonged progression-free survival. Overall survival data from that trial are not yet available.

### 4.2 Pembrolizumab

The introduction of immune checkpoint inhibitors has revolutionized the management of advanced NSCLC. Most lung cancers, in particular those associated with smoking, harbor many missense mutations and are some of the most immunogenic tumors through the presentation of neo-antigens. In many lung tumors, a T-cell response is established but is negatively regulated via the tumoral expression of checkpoint molecules. In the majority of cases of advanced NSCLC, the molecular makeup of the tumor measured by tumor mutation burden, the inflamed status of the tumor measured by markers of immune activation such as expansion of T4/T8 subsets, regulatory T-cell numbers and myeloid derived suppressor cells, and tumoral “defense” response, assessed by PD-L1 expression, provide promising biomarkers to assess candidacy for checkpoint inhibitor therapy [11].

In the pivotal Keynote-010 study, pembrolizumab was proven to prolong progression-free and overall survival compared to docetaxel in patients with PD-L1 positive (defined as PD-L1

expression on at least 1% of tumor cells) NSCLC that was previously treated with at least one line of, with a striking improvement in the subset of patients with PD-L1 expression of at least 50% [12]. This study led to FDA approval of pembrolizumab in the second line setting for PD-L1 positive (expression > 1%) tumors and provided impetus for biomarker selected first-line studies such as the Keynote-024 study. In Keynote-024, single-agent pembrolizumab was compared to standard doublet chemotherapy for patients with treatment-naïve advanced NSCLC with PD-L1 tumor proportion score (TPS) of 50% or higher. Treatment with pembrolizumab rather than chemotherapy led to a significant overall survival benefit and fewer adverse event, leading to the approval of pembrolizumab as first-line treatment for advanced PD-L1 positive ( $\geq 50\%$ ) NSCLC [13].

[figure not shown]
